To evaluate the diagnostic capacity of bladder neck opening measured by ultrasound analysis in the classification of the severity of stress urinary incontinence, a logistic regression analysis was performed. The dichotomized severity of the Sandvick test (mild/moderate versus severe/very severe) will be taken as the gold standard. Demographic and clinical variables will be evaluated as possible covariates and included in subsequent models if they had a p-value < 0.200 .

Sensitivity, specificity, Youden's index (sensitivity + specificity - 1), and positive and negative likelihood ratios (LR+ and LR-) will be calculated for bladder neck opening at rest, during the Valsalva maneuver, the variation between the two, and for the maximum model with the three variables.

The optimal cutoff point for bladder neck opening at rest will be determined using the Youden index. Subsequently, this value will be transformed into clinical units (mm) by algebraic solving of the logistic model equation, adjusted for relevant covariates (age and BMI). This approach preserves the statistical fit of the model while providing a clinically interpretable threshold.

Studentized residuals, leverage values, and Cook's distances will be estimated to identify possible outliers and influential values in the dependent variable, the predictors, and the model as a whole.

Receiver operating characteristic (ROC) curves will be constructed to determine the area under the curve (AUC). Likewise, the Hosmer-Lemeshow goodness-of-fit test will be applied to compare the observed and expected frequencies of the model (considering $p > 0.05$ as an adequate fit). The accuracy of the probabilistic predictions will be evaluated using the Brier Score (lower values indicate better performance). The

analysis will be performed using SPSS Statistics 29.0 (IBM Corp.)

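### The SAP scores its diagnostic models and its Youden-chosen rest cutoff in the women used to derive them, with no internal validation, so accuracy at data-chosen cutoffs and multivariable AUC and Brier score will on average look too good

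*Combined protocol and SAP*

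**What the plan says.** The diagnostic analysis is described in the closing paragraphs of the Statistical Analysis Plan (SAP). The reference standard is the Sandvik index, split into mild/moderate against severe/very severe.

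- Covariates: "Demographic and clinical variables will be evaluated as possible covariates and included in subsequent models if they had a p-value < 0.200". The candidates are not listed.
- Accuracy: sensitivity, specificity, the Youden index and "positive and negative likelihood ratios (LR+ and LR-) will be calculated for bladder neck opening at rest", then for the Valsalva measure, for the change between the two, and "for the maximum model with the three variables".
- Cutoff: "The optimal cutoff point for bladder neck opening at rest will be determined using the Youden index". It is then converted to mm by solving the logistic equation, "adjusted for relevant covariates (age and BMI"), to give "a clinically interpretable threshold".
- Overall performance: "Receiver operating characteristic (ROC) curves will be constructed to determine the area under the curve (AUC"), and "The accuracy of the probabilistic predictions will be evaluated using the Brier Score". A Hosmer-Lemeshow test and residual, leverage and Cook's distance checks are added.

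No bootstrap, cross-validation, split sample, shrinkage or external data set is named anywhere in the document, and nothing suggests that such text was removed. A cutoff rule is given for rest opening only. The SAP does not say whether the maximum model carries the screened covariates, or which visit and how many women enter this analysis.

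**The concern.** A cutoff picked because it maximises the Youden index in one sample will, on average, do less well in new women. A multivariable model fitted and screened on one sample likewise has a flattering AUC and Brier score there. The planned fit checks describe the same women and do not estimate performance in others.

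The Objectives section gives the study's purpose as assessing a correlation, with accurate diagnosis of severity by low-cost imaging as the hoped-for use. The SAP then aims at a threshold in mm for clinical reading. Readers would judge that threshold by its reported Youden index, sensitivity, specificity and likelihood ratios, which are the figures at risk.

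**Working it through.** **The plan's own figure.** The only stated size is 117 (39 × 3 = 117). It agrees with 27 per group inflated for 30% dropout (27/0.70 = 38.6, rounded up to 39), and also with 30 × 1.30 = 39. It cannot be derived, because no effect size is given, and it sizes the trial rather than the diagnostic analysis. Using 117 here is therefore an assumption that suits baseline data. After the dropout allowance, 117 × 0.70 = 81.9, about 82. The plan gives no accuracy figure to reproduce, so the bias was simulated.

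**Inputs, all assumed.** n = 117; 30% or 40% severe; rest opening with log-odds 0.5, 0.75 or 1.0 per SD; Valsalva correlated 0.5 with rest; Valsalva and two covariates either pure noise or informative (log-odds 0.4 each). That makes 12 settings with 1,500 data sets each, and each fitted model and cutoff was re-scored in 4,000 new women.

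**Formulas.** J = Se + Sp − 1; LR+ = Se/(1 − Sp); LR− = (1 − Se)/Sp; optimism = apparent value − value in new women.

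**Rest alone, Youden cutoff: apparent J / J in new women (ratio)**

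| Setting | log-odds 0.5 | 0.75 | 1.0 |
|---|---|---|---|
| 30% severe, noise | 0.280/0.171 (1.64) | 0.357/0.259 (1.38) | 0.423/0.333 (1.27) |
| 40% severe, noise | 0.272/0.171 (1.59) | 0.346/0.258 (1.34) | 0.415/0.332 (1.25) |
| 30% severe, informative | 0.323/0.222 (1.45) | 0.386/0.296 (1.30) | 0.451/0.363 (1.24) |
| 40% severe, informative | 0.314/0.223 (1.41) | 0.377/0.296 (1.27) | 0.437/0.359 (1.22) |

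The excess runs from 0.437 − 0.359 = 0.078 to 0.280 − 0.171 = 0.109.

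**Likelihood ratios.** In the weakest setting, LR+ is 1.74 apparent against 1.42 in new women. Since 1 − Sp = J/(LR+ − 1):
- Apparent: 0.280/0.74 = 0.378, so Se = 0.658 and LR− = 0.342/0.622 = 0.55.
- New women: 0.171/0.42 = 0.407, so Se = 0.578 and LR− = 0.422/0.593 = 0.71.

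In the setting with the smallest ratio, LR+ is 2.50 against 2.12 and LR− is 0.38 against 0.47.

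**Rest plus two covariates** (the age and BMI reading behind the mm threshold). J is 1.26-2.13 times its value in new women. AUC is 0.661 against 0.612 in the weakest setting and 0.793 against 0.778 in the strongest, so about 0.02-0.05 too high.

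**Maximum model** (simulated with rest and Valsalva as the free predictors).
- Without covariates: AUC is 0.008-0.027 too high and Brier score 0.008-0.012 too low.
- With two covariates: AUC is 0.023-0.064 too high and Brier score 0.016-0.020 too low.
- J is 1.24-1.87 times (without) or 1.28-2.34 times (with) if its cutoff is Youden-chosen. At a fixed probability of 0.5 the excess is only 0.015-0.036 or 0.04-0.07.
- Ratios near or above 2 arise only with a weak marker and pure-noise covariates.

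**Rest alone, AUC.** The difference is within about 0.005 in every setting, so there is no material optimism.

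**Outside that grid** (rest alone). At n = 82 with the same 12 settings the J ratio is 1.30-1.72. At n = 117 with 20-40% severe it is 2.05-2.27 at log-odds 0.3 and 1.16-1.20 at log-odds 1.6.

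**A second simulation with a different design** (true rest AUC 0.6-0.8; 20%, 35% or 50% severe; eight assumed noise candidates screened at p < 0.20) gave a rest J excess of 0.07-0.12 at n = 117 and 0.09-0.16 at n = 82. Multivariable AUC was too high by 0.04-0.13 and 0.06-0.17 respectively. A marker of no value (true J = 0) still showed an average apparent J of 0.11-0.14 at n = 117.

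**The case against.** The case for leaving the plan alone has four parts.

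- **Much of the analysis is unaffected.** Rest, Valsalva and change are single markers, and their unadjusted AUCs are not materially optimistic. A reader might infer that every accuracy figure in the SAP is inflated; that does not follow. A reader might also infer that the missing cutoff rules alter only the size of the bias. They can remove it: if the Valsalva and change cutoffs were fixed independently of the data, those markers' sensitivity and specificity would carry no optimism. The SAP gives no rule either way, and neither measure was simulated alone. This stands, and it limits the point.
- **The numbers are assumed.** Severe share, effect size, correlation, number of candidates and the analysis n are not in the documents. This stands for size. The direction, at a data-chosen cutoff and for multivariable fits, does not depend on them.
- **The bias is of the order of chance error.** At n = 117 the sampling SD of the apparent rest Youden index was 0.07-0.09, against a bias of 0.08-0.11. That is true, but the bias goes one way on average, and an interval centred on the apparent value would inherit it.
- **Diagnostic accuracy is not a primary outcome.** The listed primary outcomes are muscle function, ultrasound parameters and questionnaires, and the randomised comparison is untouched. This stands, and it caps the importance of the point.

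**Conclusion.** The point holds in limited form: the SAP should be changed, but the trial's treatment comparison is not at risk. Followed as written, the plan will on average overstate the accuracy of its rest-opening threshold and of its multivariable models.

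A reader might attach the 1.2-1.6 ratio to the mm threshold. That ratio is for unadjusted rest opening; the mm value comes from a model adjusted for age and BMI, for which the matching range is about 1.3-2.1, with AUC about 0.02-0.05 too high. Both ranges assume n = 117, 30-40% severe and log-odds 0.5-1.0 per SD. They should not be read as bounds: optimism is larger at n = 82 or with a weaker marker, and smaller with a stronger one.

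**What to change.** Add to the diagnostic part of the SAP:

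> In each of at least 500 bootstrap resamples, every covariate-selection, fitting and cutoff step is repeated. Optimism is the performance of the resample model and cutoff in the resample minus their performance in the original data, averaged over resamples. It is subtracted from the apparent AUC, Youden index, sensitivity and specificity and, with its sign, from the Brier score. Likelihood ratios are recalculated from the corrected sensitivity and specificity. Conclusions rest on corrected values; apparent values and a bootstrap interval for the mm cutoff are also shown.

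Also state the cutoff rule for Valsalva, change and the maximum model, and which covariates the maximum model contains, so that the steps can be repeated. The p < 0.200 screen need not be dropped for the bootstrap to work.

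Costs: no extra participants or visits; some SAP wording; a script that may have to run outside the standard SPSS menus, so the software sentence may need a second program; and less favourable reported figures. The correction is partial. In a check with 35% severe and the screen repeated in each resample, it removed 68-87% of the Youden optimism. For rest alone at log-odds 0.5, 0.277 fell to 0.204 against 0.169 in new women: (0.277 − 0.204)/(0.277 − 0.169) = 0.073/0.108 = 68%. Corrected Youden values stayed 0.02-0.05 too high. Corrected AUC lay between 0.004 below and 0.014 above its value in new women.

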STUDY PROTOCOL PLAN AND STADISTICAL ANALYSIS PLAN (SAP)

UNIVERSITY CEU CARDENAL HERRERA

Principal investigator: [name] [name]

TITLE: Second-generation Radiofrequency Application and Specific Therapeutic Exercise as a Treatment for Stress Urinary Incontinence Due to Urethral Instability. Randomised Clinical Trial

Research and Ethics Committee of CARDENAL HERRERA CEU UNIVERSITY:
CEEI25/646

NCT ID:

DATE: 01-14-2026

STUDY PROTOCOL PLAN

Objectives:

The objectives of our study have been the following:

The purpose of this study is to evaluate the correlation between urethral instability, assessed by ultrasound analysis of the bladder neck opening, and the severity of SUI, assessed by validated standard questionnaires. The determination of standard ultrasound parameters that allow urethral instability to be related to the severity of SUI would be a valuable finding for accurately diagnosing the severity of SUI using low-cost, easy-to-use imaging methods.

A randomized, single-blind clinical trial will be conducted in women with stress urinary incontinence (SUI). Participants will be randomly assigned to one of three intervention groups: radiofrequency (RF), specific pelvic floor muscle exercise (PFMT), or combined treatment (RF + PFMT). The study will be carried out at Clínica Traña (San José, Costa Rica), with an expected start date in 2025. The study will adhere to the principles of the Declaration of Helsinki and current European data protection regulations.

Adult women with urinary leakage and a bladder neck opening greater than 90°, assessed by functional ultrasound, will be included. Women with other pelvic floor disorders, pregnancy, recent treatments (RF, PFME, hormonal or laser therapies), relevant neurological, metabolic, or cardiovascular conditions, prior pelvic surgery, active infections, or contraindications to the interventions will be excluded. The estimated sample size is 117 participants (39 per group), calculated to detect statistically significant differences with 80% power and a 5% significance level, allowing for a 30% dropout rate.

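### A non-significant Hosmer-Lemeshow test, run in the data that built the model, cannot establish that the diagnostic model is adequately calibrated

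*Combined protocol and SAP*

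**What the plan says.** The goodness-of-fit paragraph at the end of the Statistical Analysis Plan says that "the Hosmer-Lemeshow goodness-of-fit test will be applied to compare the observed and expected frequencies of the model", with the decision rule "considering $p > 0.05$ as an adequate fit". The number of risk groups is not given.

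The model's outcome is binary: "The dichotomized severity of the Sandvick test (mild/moderate versus severe/very severe) will be taken as the gold standard". Demographic and clinical variables are candidates, to be "included in subsequent models if they had a p-value < 0.200". Neither the number of candidates nor the expected share of severe cases is stated. The cutoff for opening at rest is chosen by the Youden index and converted to mm by solving the logistic equation with age and BMI in it.

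The same section plans ROC curves with AUC, a Brier score without an acceptance limit, and studentized residuals, leverage and Cook's distances. It plans no calibration plot, calibration intercept or slope, linearity check or internal validation.

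The only sample size is 117 women, 39 per arm, "calculated to detect statistically significant differences with 80% power and a 5% significance level, allowing for a 30% dropout rate". It is attached to the randomised comparison, not to the diagnostic model.

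**The concern.** The rule turns failure to reject into a positive finding of fit. That is only as good as the test's power, and the plan gives no power for it. With 117 women in 10 groups there are about 12 per group, and at 30% severe about 3.5 expected events per group, so modest departures are hard to see.

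There is a second and separate problem. The test is applied to the women whose data chose the covariates and estimated the coefficients. Optimism from the p < 0.200 screen is therefore invisible to it.

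Nothing else planned fills the gap. AUC measures discrimination only, the Brier score mixes discrimination with calibration and has no limit, and the residual diagnostics look at individual observations. The Hosmer-Lemeshow rule is the only adequacy criterion with a threshold. At stake is the first stated objective, diagnosing severity by ultrasound, and the mm threshold offered for clinical use.

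**Working it through.** **Inputs from the documents.** Fit accepted at p > 0.05; covariate screen at p < 0.200; 117 women; 30% dropout. If the model used post-treatment data, 117 × 0.70 = 81.9, so about 82 women. At baseline all 117 could contribute.

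**Inputs assumed, because the documents are silent.** Ten groups; a standard normal predictor; 30% severe (varied from 15% to 70%); 2 to 15 candidate covariates; the shape and size of misfit.

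**The plan's own figure.** No effect size or SD is given, so 117 cannot be reproduced. Only the dropout step can be checked: 27/0.70 = 38.6, rounded up to 39 per arm (30 × 1.3 = 39 also fits). No error rate is stated for the Hosmer-Lemeshow test, so there is nothing to reproduce there.

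**Statistic.** With observed events O, expected events E and size n in each group, sum (O − E)²/[E(1 − E/n)] over 10 groups and refer it to chi-square with 10 − 2 = 8 degrees of freedom.

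**Check 1: omitted curvature.** The truth is logit(p) = a + 0.7x + qx², the fitted model is linear in x, 30% are severe, and n = 117. Pass rate = 1 − rejection rate:

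| q | Rejected | Passed |
|---|---|---|
| 0.3 | 14% | 86% |
| 0.5 | 38% | 62% |
| 0.7 | 68% | 32% |

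A correctly specified model was rejected 4% to 5% of the time, so the test behaves as designed. At n = 82, q = 0.3 and 0.5 pass about 90% and 75%.

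**Check 2: other sizes of misfit.** A separate simulation (prevalence about 0.40 to 0.48, 2,000 runs per scenario) grades misfit by the mean absolute error in predicted probability across deciles:

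| Misfit | Mean decile error | Pass, n = 117 | Pass, n = 82 |
|---|---|---|---|
| Quadratic 0.2 | 0.03 | 91% | 94% |
| Quadratic 0.4 | 0.07 | 79% | 85% |
| Quadratic 0.6 | 0.10 | 52% | 68% |
| Quadratic 0.8 | 0.14 | 25% | 48% |
| Quadratic 1.0 | 0.16 | 10% | 30% |
| Quadratic 1.5 | 0.22 | 0.5% | 6% |

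Omitted interactions with mean error 0.03 to 0.06 pass 82% to 91% at n = 117. A threshold step with mean error 0.10 passes 64%, and one with 0.15 passes 16%. Varying prevalence from 0.15 to 0.70 at n = 117 gives 92% to 93% for quadratic 0.2, 78% to 85% for 0.4, 50% to 72% for 0.6 and 9% to 36% for 1.0.

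**Check 3: overfitting.** One true predictor (log-odds 0.7 or 1.0 per SD) plus noise candidates screened at p < 0.200, n = 117. Among models whose calibration slope in new data fell below 0.8, 92% to 97% passed. The share of models with such a slope was about 30% to 90%, rising with the number of candidates. In a further scenario with one true predictor among 3, 6 or 10, median slopes in new data were 0.76, 0.53 and 0.38, yet about 95% passed each time. A correct model passes about 96%, so the test does not separate the two.

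**Check 4: does miscalibration move the mm threshold?** Write logit(p) = a + bx + c₁·age + c₂·BMI. With Youden probability p*, the threshold is

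x* = [logit(p*) − a − c₁·age − c₂·BMI]/b.

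Distort the linear predictor by intercept α and slope β > 0. Ranks do not change, so the Youden cut becomes α + β·logit(p*), while a becomes α + βa and the other coefficients are multiplied by β. Then

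x*′ = [α + β·logit(p*) − α − βa − βc₁·age − βc₂·BMI]/(βb) = x*.

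Numerically, (α, β) = (0, 0.5), (1, 0.5) and (−1, 2) moved the Youden probability from 0.262 to 0.373, 0.618 and 0.044, while x* stayed at −0.09988 SD throughout. The cancellation needs every coefficient to be scaled alike. It fails if c₁/b or c₂/b is distorted, or if the effect of opening is not linear.

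**The case against.** The strongest reply has four parts.

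- **Gross misfit is usually caught.** A reader might infer that badly calibrated models pass almost every time at this sample size. They do not: at n = 117, omitted quadratic terms with mean decile errors of 0.14 to 0.22 pass in only 0.5% to 25% of runs. Nor does the rule declare adequacy regardless of whether the probabilities are right. This stands.
- **The threshold and the main accuracy outputs are rank-based.** A reader might infer that the mm value depends directly on calibration, since it comes from solving the logistic equation. Check 4 shows that a pure intercept or slope error cancels. Sensitivity, specificity, likelihood ratios and AUC also rest on ranks. This stands, with the exceptions of curvature and relative coefficients.
- **The overfitting result is not a sample-size effect.** A pass rate near 95% is what in-sample testing gives at either n. This stands, and it is why a larger trial alone would not rescue the rule. How many models would be overfitted cannot be pinned down, because the number of candidates is unstated.
- **The SAP attaches no action to the result and reports other measures beside it.** True, but none of them isolates calibration, and the rule still licenses the label "as an adequate fit".

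**Conclusion.** The concern holds in this form: p > 0.05 on this test, in the development data, at about 82 to 117 women, does not establish adequate calibration. With 10 groups, 30% severe and n = 117, about 86%, 62% and 32% of models pass with mild (0.3), moderate (0.5) and strong (0.7) omitted curvature. About 92% to 97% of models overfitted through the screen also pass. These figures rest on the assumed group count, prevalence, predictor distribution and misfit shapes, and should be read as a range.

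The mm threshold is exposed only through omitted non-linearity or distorted relative coefficients for age and BMI, neither of which the rule reliably detects. The randomised comparison is unaffected. The point deserves correction before analysis because it bears on a stated aim, but it does not invalidate the trial.

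**What to change.** 1. Delete the parenthesis that equates p > 0.05 with adequate fit. If the Hosmer-Lemeshow test is kept, label it descriptive and state the number of groups.
2. Report calibration intercept and slope with 95% confidence intervals after bootstrap optimism correction, together with optimism-corrected AUC and Brier score and a smoothed calibration plot. The bootstrap must repeat the p < 0.200 screen in every resample. Uncorrected values are uninformative, because a logistic model fitted by maximum likelihood has intercept 0 and slope 1 in its own data.
3. Before solving for the mm threshold, check the linearity of bladder neck opening with a quadratic or restricted cubic spline term, and say what will be done if it is not linear.
4. List the candidate covariates and the visit whose data enter the model, so that the extent of overfitting can be judged.

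The cost is SAP wording and modest extra analysis, with no new data. Reported performance may look slightly less favourable after correction.
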